Hematologic toxicities are seen with CDK 4/6 inhibitors in general, even though neutropenia is common, the incidence of neutropenic fever is low with these treatments (19, 21, 23, 25). There are limited data on the hematologic safety profile of CDK 4/6 inhibitors in African Americans/Blacks. The PALINA study assessed the safety of palbociclib in African American/Black women with and without benign ethnic neutropenia (BEN). A polymorphism in the Duffy antigen has been implicated in the pathophysiology of BEN. A total of 35 African American/Black patients (58% with Duffy null phenotype) with a baseline absolute neutrophil count  $>1000/\mu\text{L}$  were enrolled in this phase 2 study. Women with duffy null phenotype required more dose reductions due to neutropenia; however, this did not result in treatment discontinuation or febrile neutropenia. This study showed that palbociclib is safe in African American/Black women, including those with Duffy null phenotype and baseline absolute neutrophil count 1000-1499/ $\mu\text{L}$  (26).

Transaminitis and QTc prolongation are AEs reported with ribociclib (19, 21, 23, 25). Lung toxicity is a rare but often fatal AE of CDK 4/6 inhibitors, it was reported in one patient in MONALEESA 3, and in several case reports (21).

Based on a dedicated hepatic impairment Study A2109 in healthy subjects with normal hepatic function (N=11) and volunteers with hepatic impairment (N=17), mild (Child-

22

Version 3.6 – 9/28/2023

Pugh class A; N=6) hepatic impairment did not affect the exposure of ribociclib. The mean exposure for ribociclib was increased less than 2-fold in patients with moderate, in 6 patients with Child Pugh class B AUC increased to 1.32 and 5 patients with; Child Pugh class C AUC increased to 1.34. Based on a population pharmacokinetic analysis that included 160 patients with normal hepatic function and 47 patients with mild hepatic impairment, mild hepatic impairment did not affect the exposure of ribociclib, further supporting the findings from the dedicated hepatic impairment study there are no dose reduction recommendations for patients with hepatic impairment (27).

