### 2.3 Secondary Objectives

1. To evaluate toxicity profiles (e.g., QTc prolongation, leukopenia) between each race-based cohort.
2. To characterize ribociclib pharmacokinetics in African American/Black and the Non-Hispanic White patient cohorts.
3. Conduct an exploratory candidate gene analysis of other genes with a biologically plausible role in ribociclib pharmacokinetics or therapeutic response (e.g., *CYP3A4*).

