## **3.3 Inclusion Criteria**

Patients must meet all the following inclusion criteria to be eligible for enrollment in the study:

- Signed informed consent must be obtained prior to any screening procedures that are not standard of care.
- Female  $\geq 18$  years old at the time of informed consent.
- Those who self-identify as African American or Black are eligible for that respective cohort
- Those who self-identify as non-Hispanic White are eligible for that respective cohort
- Postmenopausal or premenopausal. Patient has a known menopausal status at the time of the informed consent form signature. The patient is considered postmenopausal if: i) she has had prior bilateral oophorectomy; ii) is age  $\geq 60$  years; iii) is age  $<60$  years and has had amenorrhea for 12 or more months (in the absence of chemotherapy, tamoxifen, toremifene, or ovarian suppression) and follicle-stimulating hormone (FSH) and estradiol in the postmenopausal range per local normal ranges. All other patients who do not meet the criteria for postmenopausal status are considered premenopausal and will receive a luteinizing hormone-releasing hormone (LHRH) agonist (i.e., goserelin, leuprolide) for ovarian suppression
- Each race-based cohort has a predetermined number of patients with each CYP3A5 phenotype per the sample size calculation (section 9.1). Patients will be screen for CYP3A5 according to section 3.6.1.

- African American or Black
  - At least 3 participants who are CYP3A5 poor metabolizers
  - No more than 15 participants who are CYP3A5 intermediate or normal metabolizers
- Non-Hispanic White
  - At least 3 participants who are CYP3A5 intermediate or normal metabolizers
  - No more than 15 participants who are CYP3A5 poor metabolizers
- Patient has advanced (loco-regionally recurrent or metastatic) breast cancer not amenable to curative therapy
- Treated, stable and asymptomatic brain metastases are permitted
- ECOG performance status 0-3
- Documentation of estrogen receptor (ER) positive and/or progesterone receptor (PR) positive tumor ( $\geq 1\%$  positive stained cells) based on most recent tumor biopsy (discuss with the Principal Investigator if results in different biopsies are discordant in terms of hormone receptor positivity) utilizing an assay consistent with local standards.

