## 9.2 Statistical Analysis Plan

Primary analyses will be performed as follows. Within each race-based cohort, the ribociclib exposure which measured by ribociclib AUC will be summarized by median [Interquartile range, IQR], and two-sample t-test if normality holds or Wilcoxon-Mann-Whitney test will be used to compare AUC between CYP3A5 poor metabolizers and CYP3A5 intermediate or normal metabolizer in each independent race-based cohort. Secondary analyses will be performed as follows. Descriptive statistics will be used to characterize the data profile, frequency and percentages for categorical variables, and mean (SD) or median [IQR] for continuous variables based on the data normalization. Multiple regression will be used to identify variables associated with ribociclib AUC. To best account for any factor that may affect ribociclib exposure, covariates to be assessed include CYP3A5 metabolism status, renal function, liver function, age, race, weight, sex, among others. Any covariates with  $P < 0.2$  on univariate analysis will enter the stepwise multiple linear regression model, with  $P < 0.05$  considered statistically significant. This methodology will also be used to assess a change in absolute neutrophil count and QTc as the outcome variable. Depending on data distribution, a two-sample t-test or Wilcoxon-Mann-Whitney test will be used for 1) a change (baseline and C1D8-C1D16) in continuous variables (e.g., QTc, absolute neutrophil count) between CYP3A5 poor metabolizers and CYP3A5 intermediate or normal metabolizers, 2) to check the association between a continuous variables and categorical risk factors. Pearson correlation coefficient or Spearman correlation coefficient will be calculated to measure the association between two continuous variables. Fisher's exact test will be used for checking the association between two categorical variables. AEs will be assessed with descriptive statistics and univariate logistic regression will assess the occurrence of specific AEs with pharmacokinetic properties (e.g., AUC,  $C_{max}$ ). The approach from the linear regressions will be adapted to logistic regression to identify covariates associated with the occurrence of grade III or IV neutropenia.

Descriptive analysis of the PRO-CTCAE adverse event log to determine frequency of adverse events by race and by CYP3A5 genotype.

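### The CYP3A5 comparison of QTc and ANC change should state whether it is within cohort or pooled, and should have baseline (and race, if pooled) fixed in the model

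*Combined protocol and SAP*

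**What the plan says.** Section 9.2 contains two analyses of QTc and ANC change.

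- **Two-sample test.** A t-test or Wilcoxon-Mann-Whitney test, depending on distribution, is applied to the change from baseline to C1D8-C1D16 "in continuous variables (e.g., QTc, absolute neutrophil count) between CYP3A5 poor metabolizers and CYP3A5 intermediate or normal metabolizers". No covariate is listed and no cohort is mentioned. The primary AUC test, by contrast, is planned "to compare AUC between CYP3A5 poor metabolizers and CYP3A5 intermediate or normal metabolizer in each independent race-based cohort".
- **Regression.** After describing multiple regression for AUC, the section adds: "This methodology will also be used to assess a change in absolute neutrophil count and QTc as the outcome variable". The "covariates to be assessed include CYP3A5 metabolism status, renal function, liver function, age, race, weight, sex, among others". Covariates with P < 0.2 "on univariate analysis will enter the stepwise multiple linear regression model". The baseline value of the outcome is not named.

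Three other places bear on this. Section 3.3 sets the Non-Hispanic White quota at "No more than 15 participants who are CYP3A5 poor metabolizers", with at least 3 intermediate or normal metabolizers, and mirrors this in the African American/Black cohort. Section 1.2.4, discussing benign ethnic neutropenia (BEN) in African American/Black women, says: "A polymorphism in the Duffy antigen has been implicated in the pathophysiology of BEN". Section 2.3 lists as its first secondary objective: "To evaluate toxicity profiles (e.g., QTc prolongation, leukopenia) between each race-based cohort".

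**The concern.** The quotas make CYP3A5 status and race close to mirror images. At 3/15 and 15/3, 15 of 18 poor metabolizers are Non-Hispanic White and 15 of 18 expressors are African American/Black. A pooled, unadjusted comparison of CYP3A5 groups is then largely a comparison of races, and Section 1.5 gives possible confounding as a reason for studying the cohorts separately. The AUC test keeps that separation explicitly. The QTc and ANC test leaves it to the analyst.

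The problem depends on the reading. If the test is pooled (18 versus 18), the risk is a race difference reported as a genotype effect on toxicity. If it is within cohort (3 versus 15), there is no race confounding, but using the baseline only by subtraction gives away precision where one group has three patients.

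**Working it through.** **Inputs.** From the documents: 18 patients per cohort; phenotype split 3/15 and 15/3 (Section 3.3, at the boundary of the quotas); baseline and C1D8-C1D16 ECG and blood count, and race, all recorded (Sections 4.3.3, 4.3.9, 7.1.2). The documents give no power, SD or effect size for QTc or ANC, so there is no stated figure to reproduce. Assumed: equal SD of 1 at both visits, baseline/follow-up correlation r from 0.3 to 0.7, two-sided 5% tests, and the effect sizes below, in units of the single-visit SD. Rejection rates are simulated and good to a point or two.

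**Within cohort: gain from baseline.** The change score has variance 2(1 − r). The baseline-adjusted value has residual variance 1 − r². The ratio is (1 − r²) / [2(1 − r)] = (1 + r)/2.

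| r | Variance ratio | Power, change score | Power, baseline-adjusted |
|---|---|---|---|
| 0.3 | 0.65 | 32% | 44% |
| 0.5 | 0.75 | 43% | 52% |
| 0.7 | 0.85 | 64% | 67% |

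Power is for 3 versus 15 with a true effect of 1.2 SD. The gain shrinks to about three points at r = 0.7.

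**Pooled: confounding.** The share of a race difference carried into the CYP3A5 contrast is 15/18 − 3/18 = 2/3. False-positive rates with no CYP3A5 effect:

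| Race difference in change | Unadjusted, r 0.3 to 0.7 | With race in the model |
|---|---|---|
| 0.5 SD | about 13% to 22% | about 5% |
| 1 SD | about 33% to 61% | about 5% |

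At r = 0.5 the unadjusted figures are about 16% and 44%.

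**Pooled: a baseline difference only.** If one race is shifted equally at both visits, subtraction removes the shift and the change-score test stays near 5%. Adjusting for baseline without race then adds bias. At a 1 SD shift it rejects in about 10% to 22% of trials, worst at low r.

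**Pooled: cost of the race term.** The correlation between CYP3A5 status and race is 3/18 − 15/18 = −0.667. The variance inflation is 1/(1 − 0.667²) = 1.80. In residual SD units the standard error goes from √(1/18 + 1/18) = 0.333 to √[(1/3 + 1/15)/2] = 0.447. With baseline as well, and no race effect, the variance ratio to the unadjusted test is 1.80 × (1 + r)/2 = 1.17, 1.35 and 1.53 at r = 0.3, 0.5 and 0.7. The standard error is therefore 8%, 16% and 24% larger. The two effects cancel only at r = 2/1.80 − 1 = 0.11. At r = 0.5, a CYP3A5 effect of 0.8 SD and no race effect, simulated power is about 66% unadjusted and 52% with both terms.

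**The case against.** The strongest reply is that adjusted analysis is already planned. A reader of the two-sample sentence alone might infer that QTc and ANC get no adjustment for race; the regression in the same paragraph shows otherwise. That stands, and it narrows the point. It does not close it. Entry at P < 0.2 followed by stepwise selection does not guarantee race a place, and with a correlation of −0.667 the procedure can keep CYP3A5 and drop race. In one simulation of the rule with four irrelevant covariates added, CYP3A5 was falsely retained in about 7-10% of runs when race was the true cause. Baseline is still unnamed, and nothing says which of the two results governs.

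Other replies also stand in part:

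- **Scope.** Section 1.5 makes a within-cohort reading plausible. On that reading there is no race confounding, so the two harms cannot both be charged to the same analysis.
- **Precision.** A reader might infer that adjusting for baseline and race together sharpens the estimate. Baseline does; the race term does not, and together they usually widen the interval.
- **Benign ethnic neutropenia.** Section 1.2.4 makes a lower baseline ANC in one cohort plausible. It does not show a different change in ANC, and a stable shift does not bias a change score.
- **Secondary objective 1.** A reader might infer that Section 9.2 never compares the cohorts. However, its second use of the two-sample tests, for categorical risk factors, can cover race; the regression lists race; and adverse event frequencies are planned by race. What is missing is a named cohort contrast for QTc and ANC change.
- **Endpoint.** Section 2.4 defines the QTc endpoint as a change, which a change-score test matches. The groups are not randomised, so change-score and baseline-adjusted analyses can target different contrasts if baseline differs by genotype.

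**Conclusion.** The point holds as a gap in specification. Section 9.2 leaves the scope of the CYP3A5 comparison of QTc and ANC open, and the planned regression secures neither race nor baseline in the model. The consequence is serious only under pooling, where false positives could reach about 13-22% or 33-61% for race differences in change of 0.5 or 1 SD. Within cohort the loss is one of efficiency: 12, 9 and 3 points of power at r = 0.3, 0.5 and 0.7.

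The correlations, race differences and effect sizes are all assumed, and a split less extreme than 3/15 would lessen both the confounding and the inflation. These are secondary endpoints and only AUC is powered. The change is still worth making because it is nearly free and prevents a false genotype-toxicity finding.

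**What to change.** In Section 9.2:

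1. State that the CYP3A5 comparison of QTc and ANC is made within each race cohort, by a linear model of the C1D8-C1D16 value on CYP3A5 status and baseline value. Modelling the change on the same terms gives the identical CYP3A5 coefficient, so the endpoint in Section 2.4 is unaffected.
2. For any pooled analysis, prespecify CYP3A5 status, baseline value and race cohort as forced terms, with no P-value selection. Do not use baseline without race in a pooled model.
3. Report the adjusted difference with its 95% confidence interval. Say that baseline is included for precision and race for confounding control.
4. For secondary objective 1, report the cohort difference in QTc and ANC adjusted for baseline, with and without CYP3A5 status.

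The cost is SAP wording; no new data are needed. Each model gives up one or two degrees of freedom. The pooled CYP3A5 estimate will have a wide interval, with a standard error about 8-24% above the unadjusted one if race has no effect, and the report should say so.

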This work is focused on ribociclib but has potential implications for other medications metabolized by CYP3A. Many drugs have dosing regimens determined in predominantly White populations and thus may dosing regimens confounded by differential CYP3A5

expression. If our hypothesis is correct, it would serve as a strong similar to perform similar work in other medications metabolized by CYP3A (note, CYP3A metabolizes more drugs than any other cytochrome), particularly if no previous pharmacogenetic studies have been performed.

Two cohorts of women -one of 18 women self-identified as African American/Black and one of 18 women self-identified as Non-Hispanic White women- with HR+/HER2- metastatic breast cancer will be followed prospectively to assess the pharmacokinetics (AUC,  $C_{max}$ ,  $C_{min}$ ) and CYP3A5 pharmacogenomics in each population. We aim to identify the effect of CYP3A5 variants in the metabolism of ribociclib.

There are known race-based differences in CYP3A4 and CYP3A5; CYP3A4 is dominant in Non-Hispanic White patients and while CYP3A5 plays a larger role in African American/Black patients (32, 33). By assessing pharmacogenomics and pharmacokinetics in two separate cohorts we aim to understand the effect of CYP3A variants in the metabolism of ribociclib and to determine if there is a clinically significant correlation based on toxicity and drug concentration (assessed by AUC). We hypothesize that there will be a difference in the AUC and toxicity profile by race as the CYP3A variants in different racial groups have been well established. Also note, pharmacokinetic studies of similar size had direct clinical implications by resulting in recommended dose adjustments in the FDA label.

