Grade 3: >3.0 - 10.0 x ULN if baseline was normal; >3.0 - 10.0 x baseline if baseline was abnormal	Dose interruption of ribociclib, until resolved to ≤ grade 1, then lower 1 dose level of ribociclib. Repeat liver enzyme and bilirubin tests twice weekly for 2 weeks after dose resumption. If resolved to ≤ grade 1 in > 28 days or toxicity recurs, discontinue ribociclib.
Grade 4: >10.0 x ULN if baseline was normal; >10.0 x baseline if baseline was abnormal	Discontinue ribociclib.

Table 10: Dose Modification and Management for Neutropenia

Grade 1 or 2 (ANC 1000/mm  to LLN)	Grade 3 (ANC 500 to 1000/mm  )	Grade 3 Febrile Neutropenia	Grade 4 (ANC < 500/mm  )
No dose adjustment required	Dose interruption until recovery to Grade $\leq$ 2. Resume ribociclib at the same dose level. If toxicity recurs at Grade 3, dose interruption until recovery, then resume ribociclib at the next lower dose level.	Dose interruption until recovery of neutropenia to Grade $\leq$ 2. Resume ribociclib at the next lower dose level.	Dose interruption until recovery to Grade $\leq$ 2. Resume ribociclib at the next lower dose level.
Abbreviations: ANC, absolute neutrophil count; LLN, lower limit of normal. *Grade 3 neutropenia with single episode of fever $> 38.3^{\circ}\text{C}$ (or) above $38^{\circ}\text{C}$ for more than one hour and/or concurrent infection.			

Table 11. Dose modifications and Management for Thrombocytopenia and Anemia

Toxicity/Grade	Recommendations
Thrombocytopenia (platelet count)	
Grade 1: <75,000 mm 	No dose adjustment required
Grade 2: 50-75 mm 	Dose interruption until recovery to grade $\leq$ 1. Re- initiate ribociclib at the same dose.
Grade 3: 25-50 mm 	Dose interruption until recovery to grade $\leq$ 1. Re- initiate ribociclib at the same dose level. If toxicity recurs at grade 3: temporary dose interruption until recovery to grade $\leq$ 1 and reduces ribociclib to the next lower dose level.
Grade 4: >25 mm 	Dose interruption until recovery to grade $\leq$ 1. Re- initiate ribociclib at the next lower dose level. If toxicity recurs at grade 4: discontinue ribociclib.
Anemia (hemoglobin)	
Grade 1: $\geq 10.0$ – LLN g/dL	No dose adjustment required.
Grade 2: $\geq 8.0$ – $< 10.0$ g/dL	No dose adjustment required.
Grade 3: $< 8.0$ - $> 4.9$ g/dL, transfusion indicated	Dose interruption until recovery to grade $\leq$ 2. Re- initiate ribociclib at the same dose.

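### Section 9.2 relates adverse events to ribociclib exposure with no race-cohort or baseline term, so if the cohorts are pooled a real exposure-neutropenia association would be attenuated and could be hidden

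*Combined protocol and SAP*

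**What the plan says.** Among the secondary analyses in Section 9.2, "univariate logistic regression will assess the occurrence of specific AEs with pharmacokinetic properties", with AUC and Cmax as examples. No cohort term, stratification or baseline value is mentioned. The words that confine an analysis to within each race cohort are attached only to the primary AUC comparison.

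The next sentence treats severe neutropenia separately: the linear-regression approach is "adapted to logistic regression to identify covariates associated with the occurrence of grade III or IV neutropenia". In that approach, AUC is the outcome. The "covariates to be assessed include CYP3A5 metabolism status, renal function, liver function, age, race, weight, sex, among others", and those with P below 0.2 "on univariate analysis will enter the stepwise multiple linear regression model". Section 9.2 also says: "This methodology will also be used to assess a change in absolute neutrophil count and QTc as the outcome variable".

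Other relevant text:
- Section 1.5 makes the link between toxicity and AUC an aim, and hypothesises that AUC and toxicity differ by race.
- Section 1.2.4 cites a palbociclib study of 35 African American/Black patients, 58% of them Duffy-null. It ties Duffy to benign ethnic neutropenia and reports more neutropenia dose reductions in Duffy-null women.
- Section 3.3 admits women with ANC from 1,200/mm³. In Section 5.4, Table 10 ("Dose Modification and Management for Neutropenia") puts Grade 3 at 500 to 1000/mm³.

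**The concern.** The two cohorts are expected to differ in both exposure and susceptibility to neutropenia, in opposite directions. The cohort expected to have lower AUC is the one in which low neutrophil counts are plausibly more common. A one-predictor model fitted across both cohorts cannot separate these influences: part of the race difference in neutropenia is credited to low exposure, which pulls the slope towards the null. Neutropenia is the most common toxicity in the pivotal trials that the protocol cites, so a weak or absent slope could be read as evidence that exposure does not matter.

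**Working it through.** The documents give no power or effect figure for the exposure-AE analysis, so there is no stated figure to reproduce.

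**1. Expected AUC difference between cohorts.** The quotas in Section 3.3 and the frequencies in Section 9.1 (poor metabolizers 16% and 84.6%) imply about 3 of 18 poor metabolizers in the Black cohort and 15 of 18 in the White cohort. Section 9.1 uses a 2-fold AUC effect, which is 1.0 on the log2 scale.

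- Difference in mean log2 AUC = 1.0 × (15 − 3)/18 = 0.67.
- Ratio of geometric means = 2^(12/18) = 1.59, higher in the White cohort.
- With a 1.5-fold genotype effect: 1.5^(12/18) = 1.31.
- With no genotype effect: 1.0.

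**2. Direction of susceptibility.** Grade 3 starts at a fixed ANC. From the entry minimum, the fall needed to reach 1,000 is 1 − 1000/1200 = 17%. From an assumed baseline of 4,000 it is 1 − 1000/4000 = 75%. Lower baselines in one cohort therefore give more events there at the same exposure.

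**3. Large-sample effect of omitting race.** Model: logit(AE) = c + ln(OR per AUC doubling) × log2 AUC + ln(race OR) × Black cohort, with SD of log2 AUC 0.75 (Section 9.1) and a 2-fold genotype effect. Both odds ratios are assumptions; the documents give neither.

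| True OR per doubling | Crude OR, race OR 2 | race OR 3 | race OR 5 | race OR 10 | Race OR that makes the crude slope null |
|---|---|---|---|---|---|
| 1.5 | 1.29 | 1.18 | 1.05 | 0.90 | about 6 |
| 2 | 1.71 | 1.54 | 1.36 | 1.14 | about 17 |
| 3 | 2.53 | 2.26 | 1.96 | 1.60 | about 58 |

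With SD 0.56 (the source-study value in Section 9.1), the nulling race ORs are about 3.7, 8.4 and 23.

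**4. The same question from the ANC side.** Assumptions: 58% Duffy-null in the Black cohort; mean baseline ANC 4,000, or 2,000 to 3,000 if Duffy-null; SD of baseline ln ANC 0.3; entry at 1,200 or above. On-treatment ln ANC = ln baseline − 0.95 − slope × (log2 AUC − 0.5) + N(0, 0.3), and an event is ANC below 1,000. A slope of 0.1 means that each AUC doubling lowers ANC by a further 1 − e^(−0.1) = 9.5%.

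| Slope | Crude OR per AUC doubling | Race-adjusted OR |
|---|---|---|
| 0 (no effect) | 0.73 to 0.86 | 1.0 |
| 0.1 (weak effect) | about 1.0 to 1.26 | 1.40 to 1.48 |

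The low end of each crude range belongs to the Duffy-null baseline of 2,000. Adding baseline ANC raises the slope-0.1 figure to about 1.8. In this model AUC and baseline ANC are independent within cohort, so that last step reflects non-collapsibility of the odds ratio, not confounding. The fair comparison is crude with race-adjusted.

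**5. At n = 36** (4,000 simulated trials; true OR 2, SD 0.75, event rate 50%):

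| Race OR | Median OR, crude / adjusted | Wrong sign, crude / adjusted | Power, crude / adjusted |
|---|---|---|---|
| 1 | 2.10 / 2.14 | 4% / 5% | 37% / 32% |
| 3 | 1.57 / 2.16 | 13% / 6% | 17% / 32% |
| 10 | 1.14 / 2.14 | 36% / 7% | 4% / 26% |

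**6. Would the grade III/IV neutropenia model supply the adjusted estimate?** Neither AUC nor baseline ANC is named among its candidates, and race must first pass P < 0.2. In the step 5 simulations race passes that screen in 26%, 43% and 66% of trials at race ORs of 2, 3 and 5. The screen is weak here because the lower AUC in the Black cohort masks the race effect in a univariate test, just as race masks AUC. Stepwise selection can then still drop race.

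**The case against.** The strongest reply is that severe neutropenia, the adverse event at issue, has its own multivariable model in the next sentence, with race as a candidate, and that change in ANC and QTc receive the same method. This stands in part. A reader who stopped at the univariate sentence might infer that neutropenia has only a crude analysis, and that would be wrong. But the model does not guarantee an exposure estimate, or one adjusted for race, and the other specific AEs have only the univariate model for their relation to PK.

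Second, pooling is not stated. Section 1.5 introduces the toxicity-concentration aim by speaking of two separate cohorts, and justifies separate study by possible confounding. Within-cohort fitting would remove the problem. The text is ambiguous, but pooling is the likelier reading: only the primary analysis is confined to cohorts, and race can be a covariate only when cohorts are combined.

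Third, the AUC difference is conditional. A reader might infer that the quotas create it; they do so only if CYP3A5 status affects AUC, which is the hypothesis under test.

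Fourth, the size rests on assumed inputs. The baseline means of 4,000 and 2,000 to 3,000, the mean fall, the slope and the SDs of ANC are not in the documents, and the 58% comes from 35 patients on a different drug. The direction follows from the protocol; the magnitude is illustrative.

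Finally, this is a non-primary analysis in 36 patients. With adjustment, power for a true OR of 2 is still only about 32% at race OR 3.

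**Conclusion.** The point holds as one of attenuation. If the cohorts are pooled, the CYP3A5 hypothesis is true and neutropenia risk is higher in the Black cohort, the planned crude slope understates the exposure effect and a weak real association can vanish: about 1.0 to 1.26 crude against 1.40 to 1.48 race-adjusted under the step 4 assumptions. With no true effect, the crude estimate would look mildly protective (0.73 to 0.86 against 1.0).

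A reader might go further and infer that a real association would be reversed. The documents do not support that. In expectation, reversal needs a race OR above about 4 to 6 for a true OR of 1.5, or above about 8 to 17 for a true OR of 2. Short of that, a wrong sign at n = 36 is chance, although omitting race makes it more likely. Nor is the whole gap between about 1.0 and 1.8 bias, since part of it is non-collapsibility.

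The change is worth making because it replaces a stated method with a better one using data already collected. It does not affect the primary analysis.

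**What to change.** In Section 9.2:

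- State whether the cohorts are combined for the AE-PK analyses. Fit those logistic models with race cohort always included, using Firth penalisation when events are few.
- Show the within-cohort estimates alongside, and label univariate results descriptive.
- In the grade III/IV neutropenia model, force in AUC, cohort and baseline ln ANC, exempt from the P < 0.2 screen and stepwise removal. For QTc events, use baseline QTc in the same way.
- Label these analyses secondary or exploratory, with emphasis on intervals.

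The cost is wording plus one or two degrees of freedom and wider intervals. If race has no effect, adjustment lowers power from 37% to 32% in the step 5 setting. Three forced terms are already many for the data: event rates of 30% to 50% give about 11 to 18 events (0.30 × 36 = 10.8; 0.50 × 36 = 18), so few further covariates can be supported. No new data are needed, since race, ANC and QTc are all recorded at baseline.
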